## 5.2. Sensitivity Analyses

No sensitivity analysis is planned.

## 5.3. Subgroup Analyses

In subgroup analysis we will extend this model to test whether the following variables modify the effect of the intervention, by adding an interaction term between the treatment and the subgroup indicator. Each of these subgroups will be assessed separately.

The prespecified subgroups are:

- Gestation (<32 weeks; > 32 weeks)
- Birthweight (<1.5 kg, ≥ 1.5 kg)
- Post-natal age at enrolment (< 24 hours; > 24 hours)
- Baseline FiO2 requirement at enrolment FiO2 <0.3, FiO2 0.3-0.4; FiO2 > 0.4

The following Stata code will be used:

xtmixed y treatment##subgroup randomised\_group period site [pw = weight] || participant: period

Subgroup analyses not be done unless specifically specified. It will be done for the primary outcome and for the secondary outcome of the primary objective.

## 6. SECONDARY OUTCOMES

## 6.1 Proportion of time (over total usable time) with SpO2<90% (hypoxaemia)

This will be measured as percent time. This will be analysed in the same way as the primary outcome.

#### 6.2 Proportion of time (over total usable time) with SpO2 <80% (severe hypoxaemia)

This will be measured as percent time. This will be analysed in the same way as the primary outcome. The same subgroup analysis as specified for the primary outcome will be done.

#### 6.3 Frequency of 30s episodes with SpO2 continuously <80% (severe hypoxaemic episodes)

This will be measured as the number of episodes per hour, calculated by taking the total number of episodes each infant had, divided by the duration of the period (in hours) for that infant. This variable is expected to be left-skewed. We will report the median, with 95% confidence interval (CI), in each treatment. The two treatments will be compared using a Poisson regression model to calculate the incidence rate ratio, which will provide the percentage increase in frequency of episodes for the manual arm compared to the automated arm. The same variables will be included in a repeated measures mixed model as described for the primary outcome.

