## 3.7. Handling of Missing Data

The greatest risk of missing data will be from missing pulse oximetry reading due to disconnection or poor perfusion. Previous studies suggest that the proportion of SpO2 readings missing will be 2-4%, and very likely evenly balanced in the two study arms.

No imputation of missing data will be done. The proportions of time in each SpO2 range will be calculated using the denominator of usable time, i.e. without inclusion of time with missing SpO2 readings. For incomplete studies (i.e. infants who do not complete both phases) we will include all data of continuous pulse oximetry up to the point of cessation or ineligibility but exclude data obtained after the infant discontinued or was no longer eligible (e.g. infants who cease CPAP or who have SpO2>95% for 4 hours while in room air). We will record other clinical data (e.g. clinical outcomes and complications) for all infants irrespective of whether or not they completed one or both treatment phases.

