# 5. ANALYSIS OF THE PRIMARY OUTCOME(S)

## 5.1. Main Analysis

Primary outcome: Percent of time (over total recorded time) in the target  $SpO_2$  range (91-95%, or 91-100% when in room air).

Cross-over studies introduce risks of carry-over and period effects, and we have attempted to account for these in the study design. We consider carry-over effects to be small given that change from one mode of control to the other is instantaneous. We have allowed for a 1-hour change over period where data are not

Statistical Analysis Plan

included in the analysis. Period effects are possible with changes in practice over the study period for each infant but large changes in care over the 48 hour study period are unlikely. The clinical condition of infants will be dynamic and may change over the study period, but the primary outcome of time in target SpO2 range will be comparable irrespective of the clinical course of an infant as long as they remain on oxygen.

We will compare mean percentage time in target SpO2 range (y in code below) between the two 24 h arms of manual and automated control using weighted repeated measures mixed model linear regression adjusting for randomised group, treatment (manual vs automated), period, repeated measure in the same participant and facility (site). All infants will be included in this analysis, even those who do not provide complete studies. The weights will be calculated as the reciprocal of the total time in manual and automated control divided by 24 hours for each period separately. Infants who provide complete studies will have a weight of 1.

The following Stata code will be used:

xtmixed y treatment randomised\_group period site [pw = weight] || participant: period

We will plot the primary outcome across the treatments for individual participants using spaghetti (line) plots. The x-axis will represent manual and automated, while the y-axis will be the percent of time in target range. The colours of the lines will represent the randomisation (which treatment was received first) and complete studies will be indicated with solid lines and incomplete studies with dashed lines.

Secondary outcome for the primary objective: "Proportion of time (over total usable time) in SpO2 target range (91-95%) when receiving supplemental oxygen", measured as percent time when in oxygen, will be analysed in the same way as described for the primary outcome.

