#### The Stata code will be:

mepoisson y treatment randomised\_group period site [pw = weight] || participant: period, covariance (unstructured) irr

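### Sections 6.3, 6.7, 6.9, 6.10 and 6.11: the Poisson analysis of hourly rates uses weights that rise as observation time falls, so the shortest infant-periods have the most influence

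*SAP*

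**What the plan says.** Section 6.3 defines the outcome as a rate, "calculated by taking the total number of episodes each infant had, divided by the duration of the period (in hours) for that infant", and then states: "The two treatments will be compared using a Poisson regression model to calculate the incidence rate ratio". The command is mepoisson on y with treatment, sequence group, period and site. It ends "pw = weight] || participant: period, covariance (unstructured) irr" and has no exposure() or offset().

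The weight is defined only in section 5.1, for each period separately: "The weights will be calculated as the reciprocal of the total time in manual and automated control divided by 24 hours", with the addition "Infants who provide complete studies will have a weight of 1".

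Observation time will vary. Section 5.1 says "All infants will be included in this analysis, even those who do not provide complete studies", and section 3.7 says of incomplete studies that "we will include all data of continuous pulse oximetry up to the point of cessation or ineligibility". Section 3.7 also says that the proportions of time "will be calculated using the denominator of usable time", whereas 6.3 divides by the duration of the period.

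Sections 6.7 and 6.9, and the number of episodes in 6.10 and 6.11, are to be analysed as in 6.3.

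**The concern.** An hourly rate from 2 h of recording is far less certain than one from 24 h. A Poisson analysis normally allows for this through the exposure, so that longer records count for more. Here the outcome has already been divided by time, no exposure restores the information, and the weight runs the other way.

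Five secondary outcomes are affected. Two of them (6.10 and 6.11) come under the safety objective, where events may be rare and the loss is then greatest. The code is fixed verbatim and section 5.2 plans no sensitivity analysis, so nothing in the plan would reveal the problem.

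**Working it through.** **Inputs.** Outcome, model and code: section 6.3. Weight: section 5.1. Unequal time: sections 3.7 and 5.1. The SAP gives no episode rate and no expected share of incomplete periods; those values are assumed below. Its sample size of 13 concerns the primary outcome and plays no part here.

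**1. The weight.** The reciprocal of T/24 is 24/T. At T = 24 this is 24/24 = 1, the value that section 5.1 states for complete studies. Other readings fail: T/24 is not a reciprocal, and (1/T)/24 gives 1/576 at T = 24.

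**2. The weight that a Poisson rate needs.** For C events in T hours at rate λ, with y = C/T, the log-likelihood apart from constants is

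C·log λ − λT = T·(y·log λ − λ).

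A Poisson fit to y therefore matches the count model with exposure T only if each record has weight proportional to T. A check on one simulated data set (true ratio 2, no random effects) gave these rate ratios:
- counts with exposure: 1.916
- rate with weight T/24: 1.916
- rate, unweighted: 1.985
- rate with weight 24/T: 2.209

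**3. Size of the inversion under pure Poisson noise.** Over-weighting relative to a complete period is (24/T)/(T/24) = (24/T)².

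| T (h) | SAP weight 24/T | Needed T/24 | Ratio |
|---|---|---|---|
| 24 | 1 | 1 | 1 |
| 12 | 2 | 0.5 | 4 |
| 4 | 6 | 0.167 | 36 |
| 2 | 12 | 0.083 | 144 |

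With extra within-infant variation (assumed log-SD 0.4), Var(log rate) is about 1/(λT) + 0.16. The efficient relative weight of a 4 h record is then:
- at 0.5/h: (1/12 + 0.16)/(1/2 + 0.16) = 0.243/0.66 = 0.37, so over-weighting is 6/0.37, about 16-fold
- at 2/h: (1/48 + 0.16)/(1/8 + 0.16) = 0.181/0.285 = 0.63, so about 9-fold

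**4. Example (assumed data).** Three records: 12 events in 24 h, 12 in 24 h and 3 in 2 h.
- By exposure: 27/50 = 0.54 per hour
- Unweighted mean of rates: (0.5 + 0.5 + 1.5)/3 = 0.83 per hour
- SAP weights 1, 1, 12: (0.5 + 0.5 + 12 × 1.5)/14 = 19/14 = 1.36 per hour

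**5. Effect on precision.** Simulation of a random-intercept Poisson model. Assumptions: 40 complete infants plus 5 to 10 with a second period of 1-12 h, rate ratio 0.5, log-SD 0.8 between and 0.4 within infants, duration unrelated to rate. SD of the log rate ratio:

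| Episodes/h | As written | Counts with exposure |
|---|---|---|
| 0.2 | 0.25-0.27 | 0.14-0.15 |
| 0.5 | 0.19-0.21 | 0.11-0.13 |
| 2 | 0.12-0.14 | 0.11-0.13 |

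That is roughly 40-80% more at the two lower rates and about 10% more at 2/h. There was no material bias.

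**6. Which element does the harm.** A similar run at 0.5/h with 5 short records gave 0.218 as written, 0.137 for the unweighted rate and 0.137 for counts with exposure. Nearly all the loss comes from the weight.

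**7. Variance scale.** A Poisson likelihood for y assumes variance λ, whereas the sampling variance over 24 h is λ/24. With a random intercept, the likelihood favours a variance above zero only if the expected squared sum of an infant's two residuals exceeds the sum of its two means. Take complete periods and the log-SDs above, so that exp(0.64) − 1 = 0.8965 and exp(0.80) − 1 = 1.2255:
- mean rates 0.5 and 0.25: 1.2255 × (0.25 + 0.0625) + 0.75/24 + 2 × 0.8965 × 0.125 = 0.383 + 0.031 + 0.224 = 0.64, below 0.75, so the estimate goes towards zero
- mean rates 2 and 1: 1.2255 × (4 + 1) + 3/24 + 2 × 0.8965 × 2 = 6.13 + 0.125 + 3.59 = 9.84, above 3, so it does not

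**The case against.** Much can be said for the plan, and several stronger readings fail.

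- **A reader might infer that omitting exposure() is itself the error.** It is not. A rate weighted by T reproduces the count model, and even an unweighted rate loses little (steps 2 and 6). The fault is the rate combined with 24/T.
- **A reader might take the factor of 36 as general.** It holds only for pure Poisson noise; step 3 gives about 16 and 9 under one assumed level of extra variation. Likewise, simple weighted means without random effects give a variance 11-20 times larger, but that is not the planned model.
- **A reader might infer a biased rate ratio.** The documents do not show one. If duration is unrelated to episode rate, the loss is precision.
- **A reader might infer that the random effects always vanish.** They do so only at low rates (step 7).
- **Missing oximetry counted as episode-free time** is minor. Section 3.7 expects 2-4% missing, probably balanced. Even 2% in one arm and 4% in the other would shift the ratio by only 0.98/0.96 = 1.02.
- **Short records may be few.** Entry requires a projected need for CPAP and oxygen beyond 48 h, and recruitment continues to 40 complete studies. The simulations used a random intercept, while the SAP code adds a random period slope.

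These points limit the size of the problem. None of them justifies a weight that falls as information rises.

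**Conclusion.** The concern holds in a limited form: the weight inherited from section 5.1 runs opposite to the information in each record, in five secondary analyses. The loss of precision in step 5 is conditional on the assumed number of short records and episode rates, and is smaller with fewer short records or commoner events. With all periods complete, every weight is 1 and the rate ratio is unaffected.

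Bias is possible but not established. Section 3.7 names ceasing CPAP and sustained high saturation in room air as reasons for truncation. These reflect clinical course, so infants who stop early may have different rates; the rate ratio would then be pulled towards their short records.

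The variance-scale problem is separate and would remain at low rates (about 0.5 per hour or less) even with complete data. The primary outcome uses a different model, and safety is also reported through summaries and listings. This should be fixed, but it does not threaten the main conclusion of the trial.

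**What to change.** In 6.3, and by reference in 6.7, 6.9, 6.10 and 6.11, model the integer number of events with an exposure equal to the hours in which that event could be observed in that infant-period, and remove the time weight. For example:

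`mepoisson n_events treatment randomised_group period site, exposure(hours) || participant: period, covariance(unstructured) irr vce(robust)`

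This keeps the prespecified random effects. Define hours for each outcome:
- 6.3, 6.10 and 6.11: hours with usable SpO2.
- 6.7: hours with usable SpO2 that match the episode definition. As written, these episodes are not restricted to time in oxygen; restrict the exposure only if the sponsor so defines the episodes.
- 6.9: recorded hours in the period, because manual adjustments can occur while SpO2 is missing.

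The cost is a change to SAP wording and one line of code. It needs no new data and leaves the sample size unchanged.

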#### The Stata code will be:

mepoisson y treatment randomised\_group period site [pw = weight] || participant: period, covariance (unstructured) irr

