#### 6.9 Frequency of manual FiO2 adjustments

This is measured as number of FiO2 adjustments/hour. This will be analysed in the same way as Secondary objective 6.3.

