# 6.10 Number and duration of periods of no FiO2 increment for ≥30s with SpO2 <80% (i.e. failure to respond to severe hypoxaemia)

This is measured as number of episodes per hour and mean duration per episode. The number of episodes will be analysed in the same way as Secondary objective 6.3. For each infant the mean duration of all periods of failure to respond to severe hypoxaemia will be calculated. These means will be described and compared between the treatment arms using the same method as for the primary outcome.

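### Section 6.3 fits a Poisson mixed model to episodes per hour with no exposure term, so the rate ratio, interval and p-value of five secondary outcomes depend on the time unit

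*SAP*

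**What the plan says.** Section 6.3 (severe hypoxaemic episodes) states: "This will be measured as the number of episodes per hour, calculated by taking the total number of episodes each infant had, divided by the" length of that infant's period in hours. It continues: "The two treatments will be compared using a Poisson regression model to calculate the incidence rate ratio". The Stata command that follows is a `mepoisson` call on y with treatment, randomised group, period and site, ending "period site [pw = weight] || participant: period, covariance (unstructured) irr". It has neither `exposure()` nor `offset()`, and nothing elsewhere in the SAP supplies one.

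Four more outcomes go through the same call:

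- 6.7, hyperoxaemic episodes;
- 6.9, manual FiO2 adjustments: "This will be analysed in the same way as Secondary objective 6.3";
- 6.10, failure to respond to severe hypoxaemia: "The number of episodes will be analysed in the same way as Secondary objective 6.3";
- 6.11, severe hypoxaemia with bradycardia, in the same terms as 6.10.

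Table 9 reports all five as incidence rate ratios with confidence intervals and p-values.

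The weight comes from section 5.1: "The weights will be calculated as the reciprocal of the total time in manual and automated control divided by 24 hours for each period separately". It adds: "Infants who provide complete studies will have a weight of 1". I read this as 24/T for a period of T hours.

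**The concern.** A Poisson likelihood ties the variance to the mean of a count. Given an hourly rate, it treats a whole day of observation as one hour. In a model with fixed effects only, this would leave the rate ratio alone, because rescaling y only moves the intercept. Here there is a random intercept and a random period slope, and the likelihood must divide the observed variation between Poisson noise and those random effects. That division changes with the scale of y, and the estimate, interval and p-value change with it. The problem remains when every record lasts exactly 24 h and no signal is missing.

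At stake are the two episode-frequency outcomes, the only workload outcome (6.9) and the two safety counts that are compared between modes (6.10 and 6.11). Section 5.2 plans no sensitivity analysis that would reveal the problem.

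**Working it through.** **The plan's own figure.** The SAP gives no number for the episode outcomes. Its only computed figure is the 13 infants in section 2.6 for the primary outcome (difference 10, SD of paired difference 10, power 0.9, alpha 0.05 taken as two-sided). A paired t calculation gives power 0.883 at n = 12 and 0.911 at n = 13, so 13 is reproduced. It does not depend on this point.

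**Variance on the rate reading.** Take n = 12 episodes in T = 24 h.

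- y = 12/24 = 0.5, so the model assumes variance 0.5.
- The Poisson sampling variance of that rate is n/T² = 12/576 = 0.021.
- Ratio: 0.5/(12/576) = 24.

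The log-likelihood shows the same. Given the random effects, with hourly mean μ, a record contributes y·log μ − μ = (1/T)(n·log μ − Tμ). The bracket is the count model with exposure T, so the code divides each record's information by T.

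**Whether pw repairs this.** A weight equal to T would restore the count model. The SAP's 24/T goes the other way: relative to a complete period, a 6 h period gets 24/6 = 4 where 6/24 = 0.25 is needed, a 16-fold reversal. Reading the weight as T/24 would correct the relative weights, but a complete record would still carry 1 instead of 24.

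**The count reading.** If y is the raw count, a 6 h record is compared with a 24 h record as if they were equally long. A weight multiplies the log-likelihood, not the expected count, so it does not adjust for this. In an illustration with true ratio 1, where 30% of infants with OxyMate second and 10% with manual second stop during period 2, the mean estimated ratio was 1.07.

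**Simulation A: all records 24 h, all weights 1.** 40 infants, no treatment effect, median 0.3 episodes/h, 400 trials per scenario, robust standard errors. SDs in the first column are of the log rate, between infants / infant-by-period. Cells show SAP code vs count with exposure.

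| Assumed SDs | Empirical SD of log ratio | Median SE | Rejection under null |
|---|---|---|---|
| 1.0 / 0.4 | 0.142 vs 0.122 | 0.122 vs 0.121 | 12.2% vs 7.0% |
| 1.5 / 0.5 | 0.206 vs 0.154 | 0.145 vs 0.139 | 17.2% vs 8.0% |

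The variance ratios are (0.142/0.122)² = 1.35 and (0.206/0.154)² = 1.79. At 0.05 episodes/h the variance differed by only about 5%. Variance parameters at the boundary were dropped from the sandwich, so the rejection rates are approximate.

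**Simulation B: incomplete records included, weights 24/T.** 48 infants, 17% incomplete, true ratio 1.5 (log 0.405), 200 replicates per scenario. Cells show SAP code vs count with exposure, except the last column.

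| Rate/h; SDs | Mean log ratio | Empirical SD | Robust SE ÷ SD | Robust coverage | Model-based SE, SAP code |
|---|---|---|---|---|---|
| 1; 0.8/0.4 | 0.401 vs 0.404 | 0.129 vs 0.105 (+23%) | 0.83 vs 0.90 | 89% vs 92% | 0.161 |
| 0.1; 0.8/0.4 | 0.388 vs 0.392 | 0.229 vs 0.142 (+61%) | 0.82 vs 1.05 | 90% vs 95% | 0.489 |
| 0.3; 1.2/0.5 | 0.384 vs 0.409 | 0.192 vs 0.151 (+27%) | 0.78 vs 0.87 | 89% vs 93% | 0.251 |

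Monte Carlo error of coverage is about 2 points. Dropped fits numbered 0 to 6 for the SAP code and 0 to 39 for count with exposure, most in the third scenario.

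**Unit dependence.** Changing only hours to days moved the log ratio by a median of 0.04, 0.08 and 0.10 in the three scenarios of B. Single data sets gave 1.415 vs 1.361 and 1.409 vs 1.201. Between 36 and 103 of the 200 per-day fits did not converge, so the sizes are rough; the dependence itself follows from the likelihood above.

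**The case against.** Several points on the other side stand.

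- A reader might infer that the standard error is simply too small. The SAP does not support that without a condition. It holds for robust standard errors, which I take to follow from `pw`; model-based ones came out too large (0.161, 0.489 and 0.251 against true SDs of 0.129, 0.229 and 0.192). Part of the robust shortfall is ordinary small-sample sandwich behaviour, since the corrected model also fell to 0.87 and rejected 7-8% under the null.
- A reader might infer a biased effect. On the rate reading none of any size was seen: mean log ratio 0.38 to 0.40 against 0.405.
- Section 6.3 fixes the hour in advance, so unit dependence gives the analyst no freedom. True, but a prespecified arbitrary unit still drives the result.
- The sizes rest on assumed rates and heterogeneity, and the simulations differ for uncommon events: about 5% in variance at 0.05/h in A, but 61% in SD at 0.1/h in B. B also mixes in the reversed weights. If 6.10 and 6.11 are rare, the loss there may be small.
- Enrolment continues to 40 complete studies, so most records are of equal length and the count reading does limited damage without differential stopping.

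The usual defence, that Poisson regression with robust standard errors tolerates non-count outcomes, covers fixed-effects models. It does not cover this mixed model.

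**Conclusion.** The code is wrong as written, on either reading of y. On the rate reading the cost is a unit-dependent result, lost precision and miscalibrated intervals, not a systematic shift in the effect. The loss of precision varies widely with assumptions that the SAP does not settle, and all simulated figures are illustrative.

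A reader might conclude that the trial's safety assessment is invalid. The SAP does not support that: 6.10 and 6.11 are secondary, neither was simulated with its own event rate, and device safety is also reported through malfunction listings and event summaries (6.12, section 7, Listing 2). The primary outcome and sample size are untouched. I rate this as should-fix.

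**What to change.** For the episode counts in 6.3, 6.7, 6.9, 6.10 and 6.11, model the integer count with the hours observed in that period as exposure, drop the reciprocal-time weight, and request clustered robust standard errors explicitly, because dropping `pw` may otherwise drop them:

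`mepoisson n_episodes treatment randomised_group period site, exposure(hours) || participant: period, covariance(unstructured) vce(cluster participant) irr`

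The explicit `vce()` matters: in the third scenario of B, count with exposure covered 85% with model-based standard errors and 93% with robust ones.

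Prespecify a simpler random-effects structure, for example a participant intercept only, if the model does not converge. Keep episodes per hour for the descriptive columns of Table 9 only.

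The cost is one command and a sentence on the fallback. No new data are needed, because counts and hours already form the rate. The downside is possible non-convergence, which occurred in up to 39 of 200 simulated fits.
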